#### 1. Background

Colorectal cancer (CRC) is the second most common cancer affecting both men and women in England. The adenoma-carcinoma sequence is established as the mechanism by which adenomatous polyps develop into CRC. Detection and removal of adenomas is important in reducing CRC risk. A study which undertook single screening flexible sigmoidoscopy and adenoma clearance in patients aged 55-64, with high risk features referred for colonoscopy, reduced CRC incidence by 23% and mortality by 31%. Several clinical risk and protective factors for sporadic colorectal neoplasia (including CRC and colorectal adenomas) are recognised. Age, gender and family history of CRC are non-modifiable risk factors for the detection of advanced colorectal neoplasia. Cigarette smoking and excess body weight (EBW) are modifiable risk factors.

Obesity is increasingly prevalent in the UK, with 24.4% of men and 25.2% of women classed as obese in England. In addition to type II diabetes mellitus and increased cardiovascular risk, obesity is independently linked with increased colorectal neoplasia and recurrence of colorectal adenomas. One large European study found that up to 94% of obese individuals had non-alcoholic fatty liver disease (NAFLD), compared with 67% of overweight and 25% of normal weight patients. NAFLD is defined as fatty infiltration of the liver affecting more than 5% of hepatocytes, in the absence of alcohol excess or the consumption of steatogenic drugs. NAFLD encompasses various stages of fatty liver disease ranging from steatosis to steatohepatitis (fat + hepatocellular injury +/- fibrosis) through to cirrhosis and hepatocellular carcinoma. Obesity and type II diabetes are major risk factors for the progressive form of fatty liver, non-alcoholic steatohepatitis (NASH). At present there is no gold standard tool in screening for patients at risk of fatty liver disease, apart from identifying risk factors as mentioned above. The fatty liver index (FLI) is one such tool which incorporates height, weight, waist circumference, serum gamma-glutamyl transferase (GGT) and serum triglycerides, and if identified at high risk these patients be considered for further assessment for fatty liver with blood tests and ultrasonography. Approximately 40% of patients with NAFLD develop progressive fibrosis that can result in cirrhosis, putting patients at risk of hepatocellular carcinoma, liver failure and portal hypertension related complications. The development of advanced fibrosis (stage 3-4) in patients with NAFLD is clinically important as it is associated with a >3 fold increase risk of mortality (all-cause and liver-related) compared with a reference population. Non-invasive fibrosis scores, such as the FIB-4 score (comprising age, Aspartate aminotransferase (AST), Alanine aminotransferase (ALT) and platelet count), are reliable in diagnosing or excluding advanced fibrosis in patients with NASH and are

now widely used to identify patients with advanced fibrosis who need specialist assessment. A recent study has reported that IgA is an independent predictor of advanced fibrosis. Transient elastography, more commonly known as Fibroscan is a non-invasive imaging based technique which measures liver stiffness, and it correlates well with the degree of liver fibrosis. It is commonly used in a wide range of liver conditions including NAFLD. However its use is of limited use in patients above the age of 50, who have central obesity, those who have a body mass index (BMI) of greater than 35 or type 2 diabetes as the results may be invalid.

Additionally patients with NAFLD are at higher risk of developing cardiovascular disease and the two are strongly associated.The Qrisk 2 score is a validated tool in risk stratifying patients for cardiovascular disease. It is a score comprising of the past medical history, family history, smoking status, blood pressure, weight and height.

A 2011 Hong Kong study demonstrated a high prevalence of colorectal adenomas and advanced neoplasia in patients with NAFLD. Adenomas were found more commonly in the right colon. A subsequent systematic review and meta-analysis investigating the link between NAFLD and colorectal neoplasia in screening patients found a significant association; however, this association was more prominent in the Asian population. These studies have not been repeated in a Western population, specifically the UK. Previous studies diagnosed NAFLD using ultrasound or liver biopsy, but have not determined whether there is an association between colonic adenomas and liver enzymes and / or non- invasive markers of fibrosis, such as the FIB4 or NAFLD fibrosis score. The advantage of using liver enzymes and non-invasive fibrosis scores to identify patients with NAFLD is that they can be readily assessed on large numbers of patients and could potentially be included in risk models to predict colonic adenomas. This negates the necessity for liver biopsy- an expensive, invasive procedure with significant risk.

Approximately 400,000 colonoscopies are performed each year within the NHS for the investigation of gastrointestinal symptoms, including altered bowel habit, rectal bleeding and iron deficiency anaemia. Adenoma detection rate (ADR), defined as the number of procedures in which at least one adenoma is detected, is a widely accepted quality measure. A recent colonoscopy audit demonstrated an average polyp detection rate of 32.1%; however, ADR is variable between colonoscopists. A recent study estimated mean ADR of 15.9%. Patients found to have adenomas receive surveillance procedures, however these are currently based entirely upon number and size of adenomas with no patient factors considered. The NHS Bowel Cancer Screening Programme (BCSP)

invites all individuals aged 60-74 to undertake biennial faecal occult blood testing (FOBt). Screening is currently population based and non-targeted. Patients with a positive FOBt are invited for colonoscopy. The national Bowelscope screening programme is currently being rolled out in England and Wales, with the Lead applicants unit the first nationally to deliver this programme. All individuals aged 55 are invited for a single flexible sigmoidoscopy and adenoma clearance. Those deemed to be high risk undergo completion colonoscopy.

The mean ADR per colonoscopist within the FOBt BCSP is 46.5%, which is much higher than the symptomatic population due to the targeted nature of the programme. The BCSP has demonstrated a significant stage shift in CRC diagnosed. At present, the FOBt based screening programme is not providing protection against right sided CRC. A trial within the Scottish screening programme demonstrated that screening was an effective environment for interventions to alter patient behaviour.

In summary, although a study in an Asian population suggested an association between NAFLD and colorectal neoplasia, this has not been repeated in a Western population. It is important that the association is explored in a Western population but using non-invasive markers of liver disease and a wider range of colorectal neoplasia risk factors. This will allow development of a model to predict colorectal adenoma risk guiding screening and surveillance.

#### 2. Study Objectives

To measure the extent to which individuals with obesity and abnormal liver function are at increased risk of developing colorectal adenomas and CRC. This study aims to quantify that risk by developing a model of obesity-related and other known CRC risk factors. In addition the model will be refined using non-invasive measures of liver disease.

#### 2.1 Primary Objectives

1. To explore the link between liver enzymes, NAFLD, obesity and colorectal neoplasia in terms of adenoma burden, site and histological features

2. To assess whether the presence of liver fibrosis, measured using the FIB4 score, affects the risk of colorectal neoplasia

3. To identify which demographics contribute to increased predisposition to colorectal neoplasia

#### 3. Study Design

A multi-centre observational study will identify colorectal neoplasia burden in patients undergoing index screening or diagnostic colonoscopy. Non-invasive markers of liver disease and obesity will be assessed and a multivariate model constructed. The primary outcome is to develop a risk model with emphasis on obesity-related factors, particularly in the population with abnormal liver enzymes, to inform colorectal screening. Secondary outcomes will support this model by identifying demographics which contribute to increased predisposition to colorectal neoplasia, additionally assessing whether the presence/degree of liver fibrosis affects this risk. The link between NAFLD, obesity and colorectal neoplasia in terms of adenoma burden, site and histological features will also be explored.

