#### 3.1 Patient Recruitment

Eight Northern Regional Endoscopy Group (NREG- with a strong track record in delivering large endoscopy trials) units and Kettering General Hospital NHS Trust will recruit patients. Sites from NREG include: South Tyneside District Hospital, Freeman Hospital, Northumbria NHS Trust, Sunderland Royal Hospital, James Cook University Hospital, County Durham and Darlington Foundation Trust, Leeds Teaching Hospitals NHS Trust and North Tees University Hospitals.

Approximately 1430 patients undergoing colonoscopy as part of the BCSP or symptomatic service (most commonly patients with iron deficiency anaemia, altered bowel habit, weight loss and rectal bleeding) will be identified from endoscopy lists and recruited by a member of the research team. The final target number of participants will be refined after the first 100 participants have been recruited however this is not expected to vary significantly. Methodology by Peduzzi et al is used to calculate the minimum number of cases required to measure all variables and develop the risk model. Sample size N=10\*(k/p), where k is the number of covariates to be investigated in the model (n=15) and p the smallest of the proportions of positive or negative cases (=ADR=0.15). For non-BCSP population, ADR is around 15%; 1000 from this population are required. Minimum ADR within the BCSP is 35%; 430 cases are required to adequately power and build the model. This will allow resolution of small scale effects of covariates on risk prediction. Using Demidenko's method, the sample size needed for logistic regression with 80% power and 5% level of significance is N=8V/β2, where  $\beta$  is the natural log of the

odds ratio and V is logistic model variance due to covariates. This formula can be rearranged to determine the minimum odds ratio that can be detected at a sample size of 2000 with sufficient power. Assuming a moderate standard error in the regression (se=0.125), and calculating V from the standard error (V=(se\*vN)2) the study will have sufficient statistical power to detect an effect with a small effect size with an odds ratio of 1.42. The final sample size will be refined using data from the first 100 participants and observed effect size(s), however, the total number of recruits will not exceed 2000.

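### Sections 2.1 and 3 disagree on what is primary, and Section 3.1 separately lets the final sample size follow unnamed effects observed in only 100 participants

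*Protocol*

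**What the plan says.** Protocol Section 2.1, headed as primary objectives, has three items. The first concerns metabolic and liver exposures: "To explore the link between liver enzymes, NAFLD, obesity and colorectal neoplasia in terms of adenoma burden, site and histological features". The second turns to fibrosis: "To assess whether the presence of liver fibrosis, measured using the FIB4 score, affects the risk of colorectal neoplasia". The third is about patient characteristics: "To identify which demographics contribute to increased predisposition to colorectal neoplasia".

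Section 3 sets a different order. "The primary outcome is to develop a risk model with emphasis on obesity-related factors", with particular attention to people with abnormal liver enzymes. Then: "Secondary outcomes will support this model by identifying demographics which contribute to increased predisposition to colorectal neoplasia", and in the same sentence, "additionally assessing whether the presence/degree of liver fibrosis affects this risk". The first of the Section 2.1 items comes last here, without a label: "The link between NAFLD, obesity and colorectal neoplasia in terms of adenoma burden, site and histological features will also be explored".

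The table of contents lists a Section 2.1 with a singular primary objective and a Section 2.2 for secondary objectives. The body goes from Section 2.1 straight to Section 3.

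Section 3.1 sizes the study in two ways. The first is an events-per-covariate rule, N = 10*(k/p), for a 15-covariate model, giving about 1430. The second is a minimum detectable odds ratio of 1.42 at a sample size of 2000. On the final number it says: "The final sample size will be refined using data from the first 100 participants and observed effect size(s"). It adds that the target is not expected to change much and that recruitment will not exceed 2000.

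**The concern.** There are two separate defects.

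The first is the hierarchy. Two of the three items that Section 2.1 calls primary are secondary in Section 3, and the item that Section 3 calls primary is not on the Section 2.1 list. An analysis plan that follows one section contradicts the other, and a reader of the final report could not establish from the protocol which result was planned as primary.

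The second is the refinement rule. It uses observed effect sizes without saying which exposure or which outcome, and it takes them from 100 participants. If those estimates are mostly noise, so is the revised sample size, and nobody can check afterwards that the rule was followed.

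**Working it through.** **Side-by-side reading**

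| Item | Section 2.1 | Section 3 |
|---|---|---|
| Risk model | not listed (appears only in the Section 2 lead paragraph) | primary outcome |
| FIB-4 fibrosis | primary | secondary outcome |
| Demographics | primary | secondary outcome |
| NAFLD/obesity link with burden, site, histology | primary (with liver enzymes) | also explored; not labelled secondary |

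**The plan's own figures reproduce** (inputs from Section 3.1)

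- Events per covariate, k = 15: 10*15/0.15 = 1000 (non-BCSP) and 10*15/0.35 = 428.6, stated as 430 (BCSP). Total 1428.6, stated as about 1430.
- Detectable odds ratio: N = 8V/β² with V = (se*√N)² and se = 0.125. Substituting, β = √8 * 0.125 = 0.354 and OR = exp(0.354) = 1.42.

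N cancels in the second calculation, so the OR is 1.42 at any sample size, and the assumed standard error belongs to no named covariate. This power statement therefore does not show which effect the refinement should use.

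**How precise is an effect from 100 participants?** Assumptions, not protocol figures: one binary exposure of prevalence q, unadjusted, true OR 1.42. The overall adenoma rate follows from Section 3.1: (1000*0.15 + 430*0.35)/1430 = 21%.

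With p0 and p1 the adenoma rates without and with the exposure, solve (1−q)p0 + q*p1 = 0.21 subject to odds(p1) = 1.42*odds(p0). Then V = 1/[(1−q)p0(1−p0)] + 1/[q*p1(1−p1)], and SE = √(V/100).

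| q | p0 | p1 | V | SE of log OR at n = 100 |
|---|---|---|---|---|
| 50% | 0.181 | 0.239 | 24.5 | 0.49 |
| 25% | 0.195 | 0.256 | 29.5 | 0.54 |
| 10% | 0.204 | 0.267 | 58.0 | 0.76 |
| 5% | 0.207 | 0.270 | 107.8 | 1.04 |

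The target effect is ln 1.42 = 0.35. Even at q = 50% the standard error exceeds it: with a true OR of 1.42, the estimate from 100 participants has a 95% range of exp(0.35 ± 1.96*0.49), about 0.54 to 3.7.

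**Which effect is used also matters.** With (1.960 + 0.842)² = 7.849 for two-sided 5% and 80% power, N = 7.849*V/(ln 1.42)² is about 1563 at q = 50%, 1884 at 25%, 3702 at 10% and 6881 at 5%. The first two lie under the 2000 cap and the last two far above it.

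**Precision of the alternative, the adenoma rate.** If the first 100 split 1000:430, about 70 are non-BCSP. At a true 15%, SE = √(0.15*0.85/70) = 0.043, so the 95% range is about 7% to 23% (6.6% to 23.4%). In N = 150/p that is about 640 to 2260 for this stratum before the cap.

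**The case against.** The strongest reply is that the primary is clearer than the headings suggest. The Section 2 lead paragraph gives the aim as quantifying risk by developing a model. Section 3 names the model as primary, Section 3.1 derives 1430 from its 15 covariates, and Section 6 runs from logistic regression on adenoma presence through discrimination and bootstrapping to a predictive tool. The singular wording in the table of contents suggests, without proving it, that the three items once stood under a lost Section 2.2 heading. This stands, and it shows which way to reconcile the text. It does not remove the contradiction, because the current Section 2.1 still labels those items primary.

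A reader might infer three stronger things that the document does not support:

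- **That the refinement lets the team choose the headline exposure.** Section 3.1 uses observed effects to set the sample size, not to select a result for reporting.
- **That the labels imply a calculable inflated false-positive rate.** The protocol gives no count of separate tests. Independence would also be wrong: in Section 3.5, fatty liver is defined from ALT plus excess weight, and FIB-4 contains age, AST and ALT. Relabelling would not change the number of tests in any case.
- **That the sample size is open over the whole span from 1430 to 2000.** Section 3.1 states a cap but no floor, and expects little change.

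It is also fair to say that an adenoma rate from 100 participants is imprecise, as the working shows. The fix has to deal with that.

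**Conclusion.** Both defects hold, and they are independent: repairing one leaves the other in place.

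The conflict over what is primary can be read directly from the text and needs no assumption. It is a matter of reconciling wording rather than a missing hierarchy, since most of the protocol already treats the risk model as primary. Two of the three Section 2.1 items are explicitly made secondary; the first is demoted without that label.

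The refinement rule is poorly fixed. It names no effect, and at 100 participants the standard error of a log odds ratio is about 1.4 times (0.49/0.35) to 3 times (1.04/0.35) the effect that the study says it can detect. Those multiples rest on assumed prevalences of 50% to 5%, a single unadjusted binary exposure and a 21% overall adenoma rate. The arithmetic behind 1430 and 1.42 is not in dispute. The study remains valid, but the protocol should be amended.

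**What to change.** **Sections 2.1, 2.2 and 3.** State one primary objective: develop and internally validate the risk model for adenoma presence. Move the three current items to a restored Section 2.2 as secondary objectives, and use the same labels in Section 3, including for the NAFLD and obesity link.

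**Section 3.1.** Delete the reference to observed effect sizes. Base the refinement on the observed adenoma rate in the protocol's own N = 10*(k/p), calculated separately for the BCSP and non-BCSP strata, and keep the cap of 2000. Because the rate from the first 100 is itself imprecise, add one of two safeguards: update the rate as recruitment continues, or state that the target is not reduced below 1430 on this basis.

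**Cost.** A wording amendment, with no new data items. The association results lose primary status. Recruitment could still rise towards the existing cap if the observed adenoma rate is low.

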All potential participants will be sent or given a patient information leaflet about the study when their colonoscopy paperwork is sent or given to them, allowing adequate time to read the information leaflet (at least 24 hours) before consenting to the study. On attending the endoscopy unit for their procedure, they will be approached by a member of the research team and given the opportunity to discuss the study. Written consent will be obtained from those wishing to participate in the study. Specific consent to inform the participant's General Practitioner (GP) of participation will be obtained. Both non-consenting and consenting patients will receive their colonoscopy according to standard routine practice. Study participants will also undergo a health questionnaire, height and weight measurements and blood tests. In addition, intra-procedure data will be collected by a member of the research team onto a case report form (CRF). Any polyps detected and removed will be followed up, and histological diagnosis recorded post procedure by the research team. No additional follow-up or alteration of subsequent care is required for this study. The study will not affect the timing of outpatient appointments or results. Data will be collated and analysed by the research team. Adverse events will be classified by the chief investigators team.

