#### 3.2 Inclusion criteria

- 1. Aged 18 years and over
- 2. Able to give informed consent
- 3. Indications:
  - a. Patients with positive faecal occult blood test (FOBt) referred for index colonoscopy as part of Bowel Cancer Screening Programme
  - b. Colonoscopy conversion from Bowelscope
  - c. Index diagnostic colonoscopy due to new gastrointestinal symptoms (including but not restricted to diarrhoea, change in bowel habit, abdominal pain, PR bleeding, weight

loss), iron deficiency anaemia, family history of CRC, abnormal findings on cross sectional imaging

Recruitment materials will be produced in English; however, if language difficulties emerge in an interested patient, a professional translation service specialising in facilitating phone consultations will be used.

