#### 3.3 Exclusion Criteria

- 1. Absolute contraindication to colonoscopy
- 2. Unable to give informed consent
- 3. Known colorectal cancer
- 4. Known polyposis syndrome
- 5. Previous total/subtotal colectomy
- 6. Known colonic stricture which would prevent completion of colonoscopy
- 7. Attending for therapeutic procedure
- 8. Attending for assessment of a known lesion
- 9. Attending for assessment of known inflammatory bowel disease (IBD)
- Attending for surveillance colonoscopy (polyp surveillance, post colorectal cancer surveillance, IBD surveillance)
- 11. Colonoscopy within the last 5 years

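### One index colonoscopy in referred patients gives the prevalence of detected neoplasia; it does not support the stated aims of quantifying risk of developing it or guiding surveillance, or use before FOBt or sigmoidoscopy

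*Protocol*

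**What the plan says.** **Intended target and use.** Protocol section 2 sets out to measure how far "individuals with obesity and abnormal liver function are at increased risk of developing colorectal adenomas and CRC", and to quantify that risk with a model. Section 3 makes that model the primary outcome, with emphasis on obesity-related factors, "particularly in the population with abnormal liver enzymes, to inform colorectal screening". The Background (section 1) closes with a wider use: "This will allow development of a model to predict colorectal adenoma risk guiding screening and surveillance". Section 6 refers to the *incidence* of adenomas both for the logistic regression and for the structural equation model.

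**Design.** Section 3.2 admits "Patients with positive faecal occult blood test (FOBt) referred for index colonoscopy as part of Bowel Cancer Screening Programme", conversions from Bowelscope, and index diagnostic colonoscopy for new symptoms, iron deficiency anaemia, family history of colorectal cancer or abnormal imaging. Section 3.3 excludes "Attending for surveillance colonoscopy (polyp surveillance, post colorectal cancer surveillance, IBD surveillance") and anyone with a colonoscopy in the last five years. Section 3.1 states: "No additional follow-up or alteration of subsequent care is required for this study". Section 5 keeps participants in the study for two weeks so that blood and histology results can be retrieved. Section 6 validates the models by bootstrapping.

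**The concern.** *Developing* and *incidence* describe new lesions over time. Surveillance concerns lesions that appear after clearance. One examination without follow-up observes neither.

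The screening aim raises a related question. The Background describes the present programme thus: "Screening is currently population based and non-targeted. Patients with a positive FOBt are invited for colonoscopy". Against that description, a model to inform screening is easily read as a way of choosing whom to test, yet everyone sampled has already passed a referral step.

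What is at stake is the conclusion drawn from the model. Section 6 says that the best model will become a predictive tool, and section 10 sends the results to BSG guideline groups and the Bowel Cancer Screening Programme (BCSP). Those bodies could take the tool as evidence for surveillance intervals, or for selection before FOBt, that the study did not collect.

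**Working it through.** **Step 1. Set each stated target beside the data.**

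| Stated target | Data it would need | Data collected |
|---|---|---|
| Risk of developing adenomas and cancer (section 2); incidence (section 6) | People examined, then observed for new lesions | One index colonoscopy; two weeks in the study for result retrieval (section 5) |
| Guiding surveillance (section 1) | Findings after clearance | Surveillance attenders and colonoscopy within five years excluded (section 3.3); no study follow-up (section 3.1) |
| Informing screening (section 3), for people already referred | Screening patients at index colonoscopy | Collected: FOBt-positive patients and Bowelscope conversions (section 3.2) |
| Informing screening (section 3), before FOBt or sigmoidoscopy | A sample of those invited | None: FOBt entrants are all positive, and section 1 says Bowelscope conversion follows a high-risk finding |

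The second colonoscopy allowed in section 3.5 for anticoagulated patients does not change this, because it records polyps already seen.

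**Step 2. Reproduce the protocol's own sample size.** Section 3.1 uses N = 10 × k/p with k = 15 covariates.

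- Non-BCSP, p = 0.15: 10 × 15/0.15 = 1000, as stated.
- BCSP, p = 0.35: 10 × 15/0.35 = 428.6, stated as 430.
- Total: 1000 + 430 = 1430, as stated.

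The figures are consistent. They also show that the mix of routes comes from an events-per-variable rule and does not represent any screening population.

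**Step 3. How far absolute risk depends on referral route within the sample.**

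- Planning values, 15% against 35%: odds 0.15/0.85 = 0.176 and 0.35/0.65 = 0.538; odds ratio 3.1.
- Background values, 15.9% (a recent estimate) against 46.5% (mean per colonoscopist in the FOBt programme): ratio 46.5/15.9 = 2.9; odds 0.159/0.841 = 0.189 and 0.465/0.535 = 0.869; odds ratio 4.6.
- Planned mix: 1000 × 0.15 + 430 × 0.35 = 150 + 150.5 = 300.5 expected positives; 300.5/1430 = 21.0%.

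If the pooled model carried no information on route, directly or through its covariates, a mean prediction of 21.0% would be 21.0/15 = 1.4 times the planning rate in the non-BCSP group and 21.0/35 = 0.6 times that in the BCSP group. The protocol does not say whether route is a covariate, so this is a limiting case. It shows why one pooled performance figure is not enough.

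**Step 4. What bootstrapping can test.** Resampling measures optimism and stability in the population sampled. It contains nobody from before the referral step, so it cannot show whether the predictions hold there.

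**The case against.** The strongest reply is that the working parts of the protocol already describe the right quantity. Section 3 speaks of neoplasia burden at index colonoscopy, section 6 models whether adenomas are present or found, and the three numbered objectives in section 2.1 use neither *developing* nor *incidence*. Surveillance appears as an intended use only once, in the Background. On this view the matter is loose wording that alters no analysis. That is largely right about the analysis, and it is why the repair is small. It does not dispose of the point: section 2 states the overall aim, and the design cannot deliver it as worded.

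Reporting by route and external validation are also matters commonly left to an analysis plan or the report. Their absence is not the finding here. They follow from narrowing the claim.

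A reader might infer more than the documents support, in three ways:

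- **That no screening use is supported.** FOBt-positive attenders and Bowelscope conversions are screening-programme patients, and section 3 says only that the model will inform screening. Yield among those already referred is a legitimate use, and the associations may generate hypotheses.
- **That everyone enters because of a positive FOBt or symptoms.** Bowelscope conversion, family history and abnormal imaging are also routes, and family history need not be a consequence of the participant's own neoplasia.
- **That the 2.9-fold contrast is the error in people invited to screening.** The Background sets the FOBt programme against the symptomatic population, and patients from both sources are eligible here. The contrast shows variation within the sample only.

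**Conclusion.** The concern holds in a limited form. The aim of quantifying risk of developing adenomas and cancer, the term *incidence*, and the surveillance use are not supported by one index colonoscopy in referred patients. What the design supports is the prevalence of detected neoplasia given referral. Using its absolute risks to select people before FOBt or sigmoidoscopy would be extrapolation.

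The only size the documents allow is internal: absolute risk differs by referral route with an odds ratio of 3.1 at the planning values, or 4.6 at the Background values. No figure can be put on the error among people invited to screening, because no adenoma prevalence is given for them. The conclusion about targets rests on the eligibility and follow-up sections alone and needs no numerical assumption.

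**What to change.** - In sections 2, 3 and 6, state the target as the probability that an adenoma or neoplasia is detected at index colonoscopy in referred adults, and list all entry routes. Replace *developing* and *incidence* with prevalence terms.
- In section 1, delete surveillance as a use, or qualify it as a question for a later study with follow-up.
- In section 3, limit the screening claim to screening patients already referred for colonoscopy, both FOBt-positive and Bowelscope conversion.
- Report discrimination and calibration by referral route as well as pooled, and state that use before FOBt or sigmoidoscopy needs external validation in that population.
- Cite the detection-rate contrast only as evidence that absolute risk depends on route within the sample.

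**Cost.** Recruitment, procedures and sample size are unchanged. The indication is already confirmed from the clinical notes (section 3.5), so reporting by route needs no new data, only added analysis. The tool's claim becomes narrower and route-specific estimates are less precise: at planning values each of the two main sources supplies about 150 of the 300 expected positives. The protocol gives no expected number of Bowelscope conversions, so that route may be too small to report alone.
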